3. STUDY OVERVIEW

This is a two-part study to evaluate the PK and safety of EXPAREL in pediatric subjects aged 6 to less than 17 years. Part 1 will evaluate the PK and safety in subjects aged 6 to less than 17 years, while Part 2 will assess the safety in subjects aged 6 to less than 17 years. This is also a two-group study. Group 1 will include subjects aged from 12 to <17 years old undergoing spine surgery. Group 2 will include subjects aged from 6 to <12 years old undergoing spine or cardiac surgery. (Table 1)

In Part 1, subject enrollment will be conducted in parallel to include the older age group (12 to <17 years old; Group 1) and the younger age group (6 to <12 years old; Group 2).

Subject enrollment for Part 2 (of each group) will commence upon completion of Part 1 (of that group). In Part 2, subject enrollment will be conducted in parallel to include the older age group (12 to <17 years old; Group 1) and the younger age group (6 to <12 years old; Group 2).

Dosing of EXPAREL will be based on body weight, with a starting dose of 4 mg/kg (maximum 266 mg). Dosing of Bupivacaine HCl will be based on body weight, with a starting dose of 2 mg/kg (maximum 175 mg).

	Part 1 (PK and Safety)	Part 2 (Safety)
Group 1: subjects aged 12 to <17 years	EXPAREL 4 mg/kg [N=15]; or	EXPAREL 4 mg/kg [N = 15]; or
(Surgery: Spine Surgery)	bupivacaine HCl 2 mg/kg [N =15]	bupivacaine HCl 2 mg/kg [N =15]
Group 2: subjects aged 6 to <12 years (Surgery: Spine or Cardiac Surgery)	EXPAREL 4 mg/kg [N=15]	EXPAREL 4 mg/kg [N =15]

Part 1 (Pharmacokinetics [PK]) - Subjects aged 6 to less than 17 years

Part 1 is a multicenter, randomized, open-label study in 45 subjects aged 6 to less than 17 years of age undergoing spine or cardiac surgeries. Part 1 is divided in 2 groups: Group 1 will include subjects aged 12 to less than 17 years of age, while Group 2 will include subjects aged 6 to less than 12 years of age.

Part 1, Group 1, is an active-controlled, open-labeled, PK evaluation study in subjects aged 12 to less than 17 years undergoing spine surgery. The active comparator will be bupivacaine HCl. The planned sample size for Part 1, Group 1 is 30 subjects (15 subjects per treatment group). Subjects will be randomized 1:1 to receive either a single dose of EXPAREL 4 mg/kg (maximum 266 mg) or bupivacaine HCl 2 mg/kg (not exceeding a maximum bupivacaine HCl dose of 175 mg total) intraoperatively at the end of surgery via local infiltration.

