- Apparent clearance (CL/F) will be estimated as Dose/AUC0-∞.
- Apparent volume of distribution (Vd/F) will be estimated based on the teriminal phase as Dose/($\lambda_z \cdot AUC0-\infty$).

In addition, a population PK modeling will be performed using all PK data collected during the study. The population PK analysis plan will be developed separately.

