6.7.3 Pharmacokinetic Concentrations and Variables

A complete data listing will be provided for all PK bupivacaine concentration data. Concentrations that are BLOQ will be indicated in the listing.

A plot of bupivacaine concentration-time data, with original scale and semi-log scale overlain on the same page will be created for each individual subject.

If different than the preceding plot, a plot of dose-normalized concentration-time data, with the original scale and semi-log scale overlaid on same page, will also be created for each individual subject.

Plasma bupivacaine concentrations for each formulation will be summarized at each nominal time window (any out-of-window results would be shown only in a listing). The following descriptive statistics

will be presented: n, geometric mean, arithmetic mean, SD, %CV, median, minimum and maximum. Results will be summarized by treatment group (EXPAREL or bupivacaine HCl) for Group 1 and by surgery type (cardiac or spine) for Group 2. Plots of mean bupivacaine concentration over time will be created with the original scale and semi-log scale overlain on the same page. If the number of subjects in a group is less or equal to 3, then individual concentration over time curves will be plotted instead of the mean concentration. For group 1, there will be two plots overlain for the two treatments. For group 2, there will be two separate plots for the two types of surgery.

Pharmacokinetics parameters will be presented in the data listings and descriptive summary statistics, including the arithmetic mean, median, minimum, maximum, standard deviation, %CV of mean, geometric mean, %CV of geometric mean. Differences will be compared between the two formulations using single factor ANOVA.

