Table 14.3-5.1.2: Summary of Incidence of Serious Treatment-Emergent Adverse Events (TEAEs) (Group 2: 6 to < 12 years) - Safety Population

Table 14.3-5.1.3: Summary of Incidence of Serious Treatment-Emergent Adverse Events (TEAEs) (Both Groups: 6 to < 17 years) - Spine Surgery - Safety Population

Note to programmer: Use mock-up 14.3-4.2.1 for the following:

Table 14.3-6.1.1: Summary of Incidence of Treatment-Emergent Adverse Events (TEAEs) of Special Interest (Group 1: 12 to <17 years) - Safety Population

Table 14.3-6.1.2: Summary of Incidence of Treatment-Emergent Adverse Events (TEAEs) of Special Interest (Group 2: 6 to < 12 years) - Safety Population

Table 14.3-6.1.3: Summary of Incidence of Treatment-Emergent Adverse Events (TEAEs) of Special Interest (Both Groups: 6 to < 17 years) - Spine Surgery - Safety Population

Note to programmer: Use mock-up 14.1-5.1.1 for the following:

Table 14.3-7.1.1: Tabulation of Incidence of Prior Medications (Group 1: 12 to <17 years) - Safety Population

Table 14.3-7.1.2: Tabulation of Incidence of Prior Medications (Group 2: 6 to < 12 years) - Safety Population

Note to programmer: On these tables change the footnote 'Intraoperative medications are those indicated as such by the investigator' to read 'Prior medications are those stopped before start of study drug administration.'

Table 14.3-7.1.3: Tabulation of Incidence of Prior Medications (Both Groups: 6 to < 17 years) - Spine Surgery - Safety Population

Table 14.3-8.1.1: Tabulation of Incidence of Concomitant Medications (Group 1: 12 to <17 years) - Safety Population.

Table 14.3-8.1.2: Tabulation of Incidence of Concomitant Medications (Group 2: 6 to < 12 years) - Safety Population.

Note to programmer: On these tables change the footnote 'Intraoperative medications are those indicated as such by the investigator' to read 'Concomitant medications are those taken between the start of study drug administration and discharge from study and are not designated intraoperative medications.' Note that a concomitant medication can start prior to start of study drug and be ongoing.

Table 14.3-8.1.3: Tabulation of Incidence of Concomitant Medications (Both Groups: 6 to < 17 years) - Spine Surgery - Safety Population.

(Page X of Y)

Protocol: 402-C-319

Table 14.4-1.1: Summary of EXPAREL Pharmacokinetic Parameters (Group 1: 12 to <17 years) - PK Population

		EXPAREL	Bupivacaine HCl
	Statistic	[N=xx]	[N=xx]
AUC(0-inf) (hr*ng/mL)	n	XX	XX

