	Mean (%CV)	xx.x (xx.x)	xx.x (xx.x)
	SD	x.xx	X.XX
	Median	XX.X	XX.X
	Geometric Mean (%CV)	XX.X	XX.X
	Minimum, Maximum	XX, XX	XX, XX
	p-value *	0.xxx	
AUC(0-last) (hr*ng/mL)	n	XX	XX
	Mean (%CV)	xx.x (xx.x)	XX.X (XX.X)
	SD	x.xx	X.XX
	Median	XX.X	XX.X
	Geometric Mean (%CV)	XX.X	XX.X
	Minimum, Maximum	XX, XX	XX, XX
	p-value *	0.xxx	

* 2-sided t-test

Source: list SAS datasets used to create table SAS X.Y

ddmmmyyyyThh:mm program name

Note to programmer: Other Pharmacokinetic parameters to appear on this table are, in order of

appearance: Cmax (ng/mL), Tmax, t1/2el (hr), CL/F (L/hr), and Vd (L). Use this template also for tables:

Table 14.4-1.2: Summary of EXPAREL Pharmacokinetic Parameters (Group 2: 6 to < 12 years) - Spine Surgery - PK Population

Table 14.4-1.3: Summary of EXPAREL Pharmacokinetic Parameters (Group 2: 6 to < 12 years) - Cardiac Surgery - PK Population

Table 14.4-1.4: Summary of EXPAREL Pharmacokinetic Parameters (Both Groups: 6 to < 17 years) - Spine Surgery - PK Population

(Page X of Y)

Protocol: 402-C-319

Table 14.4-3.1: Summary of EXPAREL Pharmacokinetic Plasma Concentrations (ng/mL) (Group 1: 12 to <17 years) - PK Population

		EXPAREL	Bupivacaine HCl
	Statistic	[N=XX]	[N=xx]
15 Minutes	n	XX	XX
	Mean (%CV)	xx.x (xx.x)	xx.x (xx.x)
	SD	X.XX	X.XX
	Median	XX.X	XX.X
	Geometric Mean (%CV)	xx.x (xx.x)	xx.x (xx.x)
	Minimum, Maximum	XX, XX	XX, XX
30 Minutes	n	XX	xx
	Mean (%CV)	xx.x (xx.x)	xx.x (xx.x)
	SD	X.XX	X.XX
	Median	XX.X	XX.X
	Geometric Mean (%CV)	xx.x (xx.x)	xx.x (xx.x)
	Minimum, Maximum	XX, XX	XX, XX

Source: list SAS datasets used to create table

ddmmmyyyyThh:mm

SAS X.Y

program name

Note to programmer: Other Pharmacokinetic Plasma Concentration timepoints to appear on this table are, in order of appearance: 45 Minutes, 1 - 1.25 Hours, 2 - 3 Hours, 10 - 18 Hours, 24 - 36 Hours, and 42 - 60 Hours. Use this template also for tables:

Table 14.4-3.2: Summary of EXPAREL Pharmacokinetic Plasma Concentrations (ng/mL) (Group 2: 6 to < 12 years) - Spine Surgery - PK Population

Table 14.4-3.3: Summary of EXPAREL Pharmacokinetic Plasma Concentrations (ng/mL) (Group 2: 6 to < 12 years) - Cardiac Surgery - PK Population

Note to programmer: Change timepoints to: 15 Minutes, 30 Minutes, 45 Minutes, 1 - 1.25 Hours, 15 - 25 Hours, 30 - 40 Hours, 45 - 55 Hours, and 64 - 72 Hours.

Table 14.4-3.4: Summary of EXPAREL Pharmacokinetic Plasma Concentrations (ng/mL) (Both Groups: 6 to < 17 years) - Spine Surgery - PK Population

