program name

Note to programmer: Use this template also for the following listing, Replace "TREATMENT" with "SURGERY TYPE", followed by "Spine Surgery" or "Cardiac Surgery".

Listing 16.2-19.1.2: Medical/Surgical History (Group 2: 6 to < 12 years) - All Subjects

Listing 16.2-19.1.1: Medical/Surgical History (Group 1: 12 to <17 years) - All Subjects

Pacira Pharmaceuticals

(Page X of Y)

Protocol: 402-C-319

(Page X of Y)

Protocol: 402-C-319

Listing 16.2-20.1.1: Intraoperative Medications (Group 1: 12 to <17 years) - All Subjects

TREATME	NT: treatment-name	me				
Site	Subject	Medication Name	Dose	Unit	Route	
XXX	УУУУ	XXX	XXX.XX	(UNITS)	XXXX	
XXX	УУУУ	XXX	XXX.XX	(UNITS)	XXXX	

Source: *list SAS datasets used to create table* SAS X.Y

ddmmmyyyyThh:mm

program name

Note to programmer: Use this template also for listing:

Listing 16.2-20.1.2: Intraoperative Medications (Group 2: 6 to < 12 years) - All Subjects

(Page X of Y)

Protocol: 402-C-319

Listing 16.2-21.1.1: Study Drug Administration (Group 1: 12 to <17 years) - All Subjects

TREAT	TREATMENT: treatment-name											
Sito S	Subject	Data	Start Time	Stop Time	Incision Length	Dose	Total Volume					
SILE	Subject	Date			(cm)	(mg)	(mL)					
XXX	УУУУ	ddmmmyyyy	HH:MM	HH:MM	XX.X	XX.X	XXX					

Source:	list	SAS	datasets	used	to	create	table
SAS X.Y							

ddmmmyyyyThh:mm program_name

Note to programmer: Use this template for the following listing. Replace "TREATMENT" with "SURGERY TYPE", followed by "Spine Surgery" or "Cardiac Surgery".

Listing 16.2-21.1.2: Study Drug Administration (Group 2: 6 to < 12 years) - All Subjects

(Page X of Y)

Protocol: 402-C-319

Listing 16.2-22.1.1: Urine Drug Screen, Alcohol Blood Test and Pregnancy Test (Group 1: 12 to <17 years) - All Subjects

TREATM	ENT: treatmen	nt-name				
				Blood		
Site	Subject	Visit	Urine Drug	Alcohol	Pregnancy	
		~ ·				
XXX	УУУУ	Screening	XXXXXXXX	XXXXXXXX	XXXXXXXX	
		Day 1 (Preop)	XXXXXXXX	XXXXXXXX	XXXXXXXX	
		~ ·				
XXX	УУУУ	Screening	XXXXXXXX	XXXXXXXX	XXXXXXXX	
		Day 1 (Preop)	XXXXXXXX	XXXXXXXX	XXXXXXXX	
	***	Screening	\; \; \; \; \; \; \; \; \; \; \; \; \; \	****	***	
XXX	УУУУ	5	XXXXXXXX	XXXXXXXX	XXXXXXXX	
		Day 1 (Preop)	XXXXXXXX	XXXXXXXX	XXXXXXXX	
XXX	УУУУ	Screening	XXXXXXXX	*****	XXXXXXXX	
	ΥΥΥΥ	2				
		Day 1 (Preop)	XXXXXXXX	XXXXXXXX	XXXXXXXX	

Source: list SAS datasets used to create table SAS X.Y

ddmmmyyyyThh:mm program name

Note to programmer: Use this template also for listing:

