[figure not shown]

Figure 3.1.1 Plot of Mean (± SD) Bupivacaine Concentrations (ng/mL) over Time (Group 1: 12 to <17 years) - PK Population - Semi-logarithmic Scale

Note to programmer: Overlay both treatments for Group 1. Change the y-axis label to "Log(Bupivacaine Concentration (mg/mL))". Use this template for the following figure:

[figure not shown]
Figure 3.1.2 Plot of Mean (± SD) Bupivacaine Concentrations (ng/mL) over Time (Group 2: 6 to < 12 years) - Spine Surgery - PK Population - Semi-logarithmic Scale

Figure 3.1.3 Plot of Mean (\pm SD) Bupivacaine Concentrations (ng/mL) over Time (Group 2: 6 to < 12 years) - Cardiac Surgery - PK Population - Semi-logarithmic Scale

Figure 3.1.4 Plot of Mean (± SD) Bupivacaine Concentrations (ng/mL) over Time (Both Groups: 6 to < 17 years) - Spine Surgery - PK Population - Semi-logarithmic Scale

Figure 4.1.1 Plot of Individual Bupivacaine Concentrations (ng/mL) over Time (Group 1: 12 to <17 years) - PK Population - Linear-Linear and Log-Linear

Note to programmer: Modify the figures below as follows: Combine each pair of figures for individual subjects into one figure. Put log-linear scale on right hand side x-axis. Overlay two lines on one figure.

Note to programmer: *Use this template for the following figures:*

Figure 4.1.2 Plot of Individual Bupivacaine Concentrations (ng/mL) over Time (Group 2: 6 to < 12 years) - PK Population - Cardiac Surgery - Linear-Linear and Log-Linear

Figure 4.1.3 Plot of Individual Bupivacaine Concentrations (ng/mL) over Time (Group 2: 6 to < 12 years) - PK Population - Spine Surgery - Linear-Linear and Log-Linear

Figure 4.1.4 Plot of Individual Bupivacaine Concentrations (ng/mL) over Time (Group 1: 12 to <17 years) - PK Population - Linear-Linear and Log-Linear

Note to Programmer: If there is a lot of dose variation (i.e. a lot of departure from 4 mg/kg EXPAREL or Bupivacaine HCl 2 mg/kg), add figures for dose normalized concentration.

Note to programmer: *Use Figure 2.1.1 for the figures below.*

Figure 5.1.1 Plot of Mean (± SD) Numeric Rating Scale at Rest Pain Intensity Scores over Time (Group 1: 12 to <17 years) - Safety Population

Note to programmer: *Replace label on y-axis with "NRS-R". Overlay both treatments for Group 1.*

Figure 5.1.2 Plot of Mean (\pm SD) Color Analog Scale Pain Intensity Scores over Time (Group 2: 6 to < 12 years) - Safety Population

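### The Group 1 AUC and Cmax p-values are labelled a comparison of formulations, but the arms also differ in dose (4 versus 2 mg/kg), so they compare exposure at the study doses only

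*SAP*

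**What the plan says.** The SAP adds a noncompartmental analysis (NCA) and, at the end of section 6.7.3, a between-arm test of its parameters: "Differences will be compared between the two formulations using single factor ANOVA". No analysis scale, dose covariate or dose-normalised parameter is named.

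Only Group 1 contains both products. SAP section 3 randomises it 1:1 to "EXPAREL 4 mg/kg (maximum 266 mg) or bupivacaine HCl 2 mg/kg (not exceeding a maximum bupivacaine HCl dose of 175 mg total"), with 15 per arm in Part 1.

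The shell for Table 14.4-1.1 starts with "AUC(0-inf) (hr*ng/mL"), then AUC(0-last) in the same units, each followed by a p-value row footnoted as a two-sided t-test. The programmer note extends the table to "Cmax (ng/mL), Tmax, t1/2el (hr), CL/F (L/hr), and Vd (L"). Neither AUC nor Cmax is expressed per mg or per mg/kg.

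Dose adjustment appears in two other places:
- **Plots.** Section 6.7.3 provides for "a plot of dose-normalized concentration-time data" for each subject where it would differ from the unadjusted plot. A figure note says to "add figures for dose normalized concentration" if doses depart much from nominal.
- **Clearance.** Section 6.7.2: "Apparent clearance (CL/F) will be estimated as" dose divided by AUC(0-inf). CL/F is on the same table.

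**The concern.** Every EXPAREL subject in Group 1 has one formulation at one mg/kg level, and every control has the other formulation at half that level. A one-factor model has a single contrast, and that contrast carries both differences. The label promises an answer about formulation that AUC and Cmax in raw units cannot give.

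The misreading can go either way. A small p-value may be taken as a formulation effect when twice the dose is enough to produce it. A large p-value may be taken as no formulation effect when a lower exposure per mg has been offset by the higher dose. SAP section 1 allows the planned analyses to be used in study reports, submissions and manuscripts, where the label would travel with the p-value.

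**Working it through.** **1. Inputs.** From the SAP: 15 per arm, 4 versus 2 mg/kg, caps of 266 and 175 mg, one-factor ANOVA or two-sided t-test. The group size can only be checked as a count (15 + 15 = 30), because it rests on a PK precision that is not stated. Assumed, because neither document gives them: CV 30, 50 and 80%, log-normal exposure, dose proportionality, significance level 0.05.

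**2. ANOVA or t-test.** With two groups the two tests are the same. A check on one simulated data set gave p = 0.5719 both ways. The text and the shell do not conflict here.

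**3. Dose ratio at equal weight w.** Ratio = min(4w, 266) / min(2w, 175). The caps start to act at 266/4 = 66.5 kg and 175/2 = 87.5 kg.
- up to 66.5 kg: 2.00
- 70 kg: 266/140 = 1.90
- 80 kg: 266/160 = 1.66
- from 87.5 kg: 266/175 = 1.52

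The ratio never reaches 1.

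**4. What the contrast estimates.** Under dose proportionality, the difference in mean log exposure is ln(dose ratio) + ln(per-mg ratio). Only the sum can be estimated.

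**5. Equal exposure per mg, ratio 2.00.** The shift is ln 2 = 0.693. On the log scale the standard error is sqrt(ln(1 + CV²)) × sqrt(2/15) = 0.107, 0.172 and 0.257 at the three CVs. The shift is therefore about 6.5, 4.0 and 2.7 standard errors. Simulation (200,000 trials per cell) gives p<0.05 in:
- untransformed, unadjusted: 100, 95 and 64%
- log scale, unadjusted: 100, 97 and 74%
- log scale, dose-normalised: about 5% throughout

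**6. EXPAREL halves exposure per mg.** The shift is ln(2 × 0.5) = 0. The unadjusted test rejects in about 5, 5 and 4% of trials; the log dose-normalised test rejects in 100, 97 and 74%.

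**7. What CL/F covers.** With equal exposure per mg (40,000 trials), CL/F gives p<0.05 in 5, 5 and 4%. AUC(0-inf) is significant and CL/F is not in 95, 92 and 61%, if all subjects are estimable. Section 6.7.2 requires at least three points after Cmax for the terminal slope. The spine schedule has eight samples, so a scheduled Cmax at sample 6 (10–18 h) or later leaves at most two. Such a subject has neither AUC(0-inf) nor CL/F unless unscheduled samples help; only Cmax and AUC(0-last) remain, and neither has a dose-adjusted form.

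**8. Sensitivity to the caps (equal exposure per unit dose).**
- Weights assumed uniform from 40 to 80 kg, exposure following mg/kg received: mean ratio 1.94; rejection in 100, 94 and 60%.
- Every subject at 87.5 kg or more, ratio 1.52: 96, 60 and 29%. This is only a bound. At the upper BMI limits in Protocol Appendix 5, 87.5 kg requires a height from sqrt(87.5/28.9) = 1.74 m (girl of 16) to sqrt(87.5/24.2) = 1.90 m (boy of 12).

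**The case against.** The strongest reply is that this turns on one word. Section 6.7.3 uses formulation and treatment almost interchangeably for the arms, and nothing says the p-value will be read per mg. As a comparison of the regimens as given, the test is valid. That stands, and it is why relabelling is a sufficient remedy. It does not remove the fault, because a reader of the table has only the label to go by.

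Second, CL/F already gives the dose-adjusted comparison. This stands for AUC(0-inf) where the slope is estimable, and a significant AUC(0-inf) beside a non-significant CL/F would show an attentive reader that dose explains the difference. A reader might infer that the plan has no dose-adjusted comparison at all; the documents do not support that. The gap is Cmax and AUC(0-last).

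Third, the 100, 95 and 64% assume equal exposure per mg. That suits AUC better than Cmax: Protocol 7.3 describes slow release with peaks at roughly 0–2 h and 24–48 h. Even AUC(0-last) is uncertain, because spine sampling ends at 42–60 h. For Cmax the halved case is the more plausible one, and there a null result is a correct statement about exposure at the study doses. It is wrong only as a statement about formulation.

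Fourth, Table 14.4-1.4 (spine surgery, both age groups) reuses the shell. A reader might infer a planned contrast that adds non-randomised 6 to <12 year-olds to the EXPAREL side. The documents do not show this: the same shell also serves Tables 14.4-1.2 and 14.4-1.3, which are EXPAREL only and can hold no such contrast, so reuse is not evidence of a planned test.

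**Conclusion.** The point holds for AUC(0-inf), AUC(0-last) and Cmax in Group 1. Their p-values compare exposure at the study doses and cannot be attributed to formulation. AUC(0-inf) has a partial remedy in CL/F; Cmax and AUC(0-last) have none.

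The rejection rates illustrate the size. They depend on the assumed CVs, dose proportionality and 0.05 level. The ratio 2.00 is in nominal mg: Protocol 7.3 gives EXPAREL as bupivacaine base, while the base or salt convention for the comparator is not stated.

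A reader might infer that the trial's main PK conclusions are at risk. They are not. The NCA is additional to the population PK analysis, no decision rule uses the p-value, the Protocol plans no formal testing, and EXPAREL's own estimates do not depend on the contrast. The separate population PK plan is not available here, so its handling of dose cannot be judged. This should be corrected before the tables are produced, but it is not critical.

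**What to change.** For Group 1 only, in SAP 6.7.3 and Table 14.4-1.1, do one of the following:

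- Relabel the AUC and Cmax p-values as a descriptive comparison of exposure at the study doses, or drop those rows.
- If a formulation comparison is wanted, base it on log dose-normalised Cmax and AUC(0-last), using the dose actually given. Report the EXPAREL to bupivacaine HCl geometric mean ratio with a confidence interval, labelled descriptive. State the normaliser (mg or mg/kg), the dose-proportionality assumption and the comparator's base or salt convention.

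Optionally, add a programmer note that Table 14.4-1.4 carries no between-formulation p-value.

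The cost is SAP wording and a few shell rows. No new data are needed: dose in mg is already in "Listing 16.2-21.1.1: Study Drug Administration (Group 1: 12 to <17 years) - All Subjects", and weight has its own listing. The downside of the ratio is that it rests on dose proportionality, which the documents do not establish. Its precision would also be modest. The 90% interval factor is exp(1.701 × sqrt(ln(1 + CV²)) × sqrt(2/15)) = 1.20, 1.34 and 1.55 at CV 30, 50 and 80%. If exposure follows mg/kg but is divided by mg, weight adds variance (SD of log weight about 0.20 for uniform 40–80 kg) and the factors become about 1.25, 1.37 and 1.57. That is why the normaliser should be fixed in advance.

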7.3. EXPAREL (bupivacaine liposome injectable suspension)

Bupivacaine is one of the longer-acting local anesthetics, but even so it has a limited duration of action after local administration, usually less than 8 hours. EXPAREL is a bupivacaine liposome injectable suspension. It consists of microscopic spherical, multivesicular liposomes (DepoFoam[®] drug delivery system), organized in a honeycomb-like structure comprising numerous non-concentric internal aqueous chambers containing a bupivacaine base at a concentration of 13.3 mg/mL. Each chamber is separated from adjacent chambers by lipid membranes. The lipids (phospholipids, cholesterol, and triglycerides) are naturally occurring or close analogs of endogenous lipids. Bupivacaine is slowly released from the DepoFoam particles by a complex mechanism involving reorganization of the barrier lipid membranes and subsequent diffusion of the drug over an extended period of time. EXPAREL has been noted in infiltration studies to have a bimodal curve (Apseloff 2013), with an initial peak occurring at approximately 0 to 2 hours and a second peak at approximately 24 to 48 hours (Hu 2013).

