15.1. Study Hypothesis

No formal hypothesis testing will be conducted.

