6.11 Deviations from the Protocol

This SAP has an additional analysis that was not specified in the Protocol. Pharmacokinetic parameters will be calculated with a NCA method as specified in Section 6.7.2.

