Figure 1.1.1 Plot of Time to First Rescue Medication Use (Group 1: 12 to <17 years) - Safety Population

[figure not shown]
Note to programmer: Time to first rescue on x-axis 0-72 Hours by 12. Overlay both treatments for Group 1. For table underneath plot, provide for each treatment in Group 1 with a header for treatment. Add footnote: "Subjects who are not administered an opioid rescue medication by 72 hours are censored at 72 hours after surgery or at the time of last follow-up, whichever is earliest."

Use this template for the following figure:

Figure 1.1.2 Plot of Time to First Rescue Medication Use (Group 2: 6 to < 12 years) - Safety Population

Note to programmer: Time to first rescue on x-axis 0-72 Hours by 12. Overlay both surgery types for Group 2. For table underneath plot, provide for each surgery type in Group 2 with a header for surgery type. Add footnote: "Subjects who are not administered an opioid rescue medication by 72 hours are censored at 72 hours after surgery or at the time of last follow-up, whichever is earliest."

Figure 2.1.1 Plot of Mean (± SD) Bupivacaine Concentrations (ng/mL) over Time (Group 1: 12 to <17 years) - PK Population - Linear Scale

Note to programmer: Overlay both treatments for Group 1. For Samples 4-8, use the midpoint of the collection window for the tick mark (i.e. 1.125 for 1-1.25 window). Label the tick mark with the time window (i.e. "1-1.25 hr"). Change the y-axis label to "Bupivacaine Concentration (mg/mL)".

Add footnotes: "For concentrations below the limit of quantification (BLOQ), pre-dose values are set to zero, BLOQ values between the dosing time and the first time point above lower limit of quantification (LLOQ) are set to 0, BLOQ values at time points between two measurable concentration values are set to ½ of LLOQ (lower limit of quantification), and all remaining BLOQ values are set to missing. For Samples 4-8, the midpoint of the collection window is used for the tick mark. "

Use this template for the following figures:

Figure 2.1.2 Plot of Mean (± SD) Bupivacaine Concentrations (ng/mL) over Time (Group 2: 6 to < 12 years) - Spine Surgery - PK Population - Linear Scale

Figure 2.1.3 Plot of Mean (\pm SD) Bupivacaine Concentrations (ng/mL) over Time (Group 2: 6 to < 12 years) - Cardiac Surgery - PK Population - Linear Scale

Figure 2.1.4 Plot of Mean (± SD) Bupivacaine Concentrations (ng/mL) over Time (Both Groups: 6 to < 17 years) - Spine Surgery - PK Population - Linear Scale

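### The SAP adds PK t-test and log-rank p-values that the protocol does not plan and SAP 6.11 does not declare; the PK tests state no scale or dose normalisation and extend to mean Tmax

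*SAP*

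**What the plan says.** Protocol 15.1 states "No formal hypothesis testing will be conducted". Section 15.7 marks significance testing as not applicable. Section 15.6.3 plans a population PK model with listings and descriptive statistics for the parameters.

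SAP 6.7.3 ends with "Differences will be compared between the two formulations using single factor ANOVA". It names no transformation, effect measure, interval or significance level. The sentence before it asks for both arithmetic and geometric means with their CVs.

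Shell 14.4-1.1 carries a p-value row, footnoted as a two-sided t-test, under AUC(0-inf) and AUC(0-last). Its programmer note extends the template to "Cmax (ng/mL), Tmax, t1/2el (hr), CL/F (L/hr), and Vd (L"). The same template serves 14.4-1.2 and 14.4-1.3 (Group 2, by surgery type) and 14.4-1.4 (both groups, spine surgery).

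SAP 6.9.2.1 places a log-rank p-value on the Group 1 Kaplan-Meier plot of time to first opioid.

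SAP 6.11 begins "This SAP has an additional analysis that was not specified in the Protocol" and names one item, the non-compartmental calculation of 6.7.2.

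**The concern.** A reader comparing the final report with the protocol would find p-values that the protocol excluded and that the SAP's own section on departures omits. That is a traceability problem whatever the results.

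The PK p-values are also poorly defined. Group 1 of Part 1 (15 per arm) is the only randomised PK contrast. As written, it yields a p-value for equality of means on an unstated scale, between arms given different mg/kg doses, with no ratio or interval, although SAP 6.10.1 justifies the sample size by precision. For Tmax the protocol expects an EXPAREL profile with an "initial peak occurring at approximately 0 to 2 hours and a second peak at approximately 24 to 48 hours", and a mean is a weak summary if children divide between those peaks. In Group 2 there is no second formulation to compare.

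**Working it through.** The documents give no significance level, effect size or CV for this comparison, so there is no stated figure to reproduce.

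**Step 1. Planned against declared.**

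| Analysis | Protocol | SAP | Listed in 6.11? |
|---|---|---|---|
| Non-compartmental PK | Not planned (15.6.3: population model) | 6.7.2 | Yes |
| ANOVA / t-test on PK | None (15.1, 15.7; 15.6.3 descriptive) | 6.7.3, shell 14.4-1.1 | No |
| Log-rank, first opioid | None (15.1, 15.7) | 6.9.2.1 | No |

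PK p-values in shell 14.4-1.1: 2 AUCs + 5 further parameters = 7. At an assumed level of 0.05, and if the tests were independent, the chance of at least one false positive is 1 − 0.95^7 = 30.2%. The parameters are correlated, so this is a rough upper figure.

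**Step 2. ANOVA or t-test.** With two arms, F = t² for the pooled t-test, so the two labels agree. In one simulated data set (15 per arm) both gave p = 0.0449, and the unequal-variance t-test gave 0.0486. The labels conflict only if the latter is meant.

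**Step 3. Scale.** The SAP writes out a log step where it wants one: the terminal-slope regression (6.7.2) and total opioid dose (6.9.2). It writes none for the PK comparison, and the shell lists original units. A programmer would therefore use raw values. The illustration below is wholly assumed: lognormal data, 15 per arm, equal CVs, true geometric ratio 2, two-sided 0.05, 20,000 to 40,000 simulations per case.

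| CV | Power, raw | Power, log |
|---|---|---|
| 30% | 100% | 100% |
| 40% | over 99% | over 99% |
| 60% | 86% | 91% |
| 80% | 64% | 74% |
| 100% | 46% | 60% |

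With true geometric ratio 1, raw rejection is 4-5% when CVs are equal. It rises to 9.0% with CVs of 30% and 100% (log: 5.6%). In that last case the arithmetic means do differ (ratio 1.35), so it is a false positive only if the geometric ratio is the target.

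**Step 4. Dose.** Nominal dose ratio: 4 / 2 = 2. If apparent clearance were the same for both products, AUC = dose / (CL/F) would have a ratio near 2 from dose alone. By the same simulations at CV 50%, a test of equal AUC would then reject in 95% (raw) or 97% (log) of trials. The caps change the ratio in heavier children: EXPAREL reaches its cap at 266 / 4 = 66.5 kg and bupivacaine HCl at 175 / 2 = 87.5 kg, and from 87.5 kg the dose ratio is 266 / 175 = 1.52. Of the parameters, CL/F and Vd/F already divide by dose; AUC and Cmax do not.

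**Step 5. Tmax.** Assume early peaks at 0.6 h, late peaks at 36 h, and a fraction f late: mean = (1 − f) × 0.6 + f × 36.
- f = 0.5: mean 18.3 h, SD 0.5 × 35.4 = 17.7 h. No child in this example peaks near the mean.
- f = 0.9: mean 32.5 h, inside the expected late window.

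A rank-based shift does not rescue the even split. In simulation with 15 per arm, the Hodges-Lehmann difference fell below 2 h in about half of trials and above 20 h in the other half. The median can flip in the same way, so a count of early and late peaks has to accompany it.

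**The case against.** Several points on the other side stand.

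- **Wrong scale.** A reader might infer that the SAP analyses untransformed data. It does not say so; it is silent, and it asks for geometric means. The supportable statement is that the scale is unspecified, with raw as the default.
- **Lost power.** A reader might infer a material loss from raw analysis. That depends on CVs the documents do not give, and the gap is negligible at 30-40%. Power is also a secondary yardstick for a test the protocol never planned.
- **Dependence on the more variable arm.** With geometric ratio 1.5 and CVs of 40% and 80%, raw power is 28% or 57% depending on which arm is more variable, while log power stays at 47%. Fix the arithmetic ratio at 1.5 instead and log power moves from 77% to 19% and raw from 55% to 28%. This shows a choice of target quantity, not a fault peculiar to raw data.
- **Mean Tmax where nobody peaks.** Protocol 7.3 describes a bimodal concentration curve. It does not say that children split between early and late Tmax, so the 50/50 case is hypothetical. The shell already prints median, minimum and maximum.
- **No comparison possible without the p-value.** The shell shows geometric means for both arms side by side, so a point ratio can be derived. What is missing is its interval. The protocol's own PK analysis, the population model, is reported separately.
- **Figures.** The shell titled "Plot of Mean (± SD) Bupivacaine Concentrations (ng/mL) over Time (Group 1: 12 to <17 years) - PK Population - Semi-logarithmic Scale" might suggest lower error bars that cannot be drawn. Its axis note refers to log concentration, so it is unclear which values are averaged, and the defect is not established. The mg/mL axis notes under ng/mL titles are clerical.

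None of this answers the conflict with protocol 15.1 and 15.7, the omission from 6.11, or the unstated dose handling.

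**Conclusion.** The point holds as a documentary inconsistency with an under-specified analysis attached. Seven PK p-values and one log-rank p-value are planned against a protocol that excludes testing, and 6.11 declares none of them. That part rests on the text alone. The absence of a stated scale, interval and dose normalisation also rests on the text.

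The numerical consequences rest on assumptions: lognormal parameters, CVs of 30-100%, 15 evaluable children per arm and, for the dose argument, equal apparent clearance. On these, the choice of scale ranges from immaterial (CV 30-40%) to about 10 points of power (CV 80%, ratio 2). Dose is the more basic issue: a test of equal AUC or Cmax can reject because of the dose difference and say nothing about formulation. The t-test on Tmax is hard to interpret if both peaks occur as Tmax.

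PK is the primary objective, so this should be corrected. The study remains descriptive and the population model continues separately, so the point does not undermine the trial.

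**What to change.** 1. Delete the ANOVA sentence from SAP 6.7.3 and the p-value rows from shells 14.4-1.1 to 14.4-1.4. In Group 2, which is single-arm, a formulation p-value has no meaning.
2. For Part 1 Group 1, report the EXPAREL / bupivacaine HCl geometric mean ratio with 95% confidence interval from log-transformed AUC and Cmax, both as observed and normalised to the dose actually given, and CL/F. Per mg, the dose-normalised AUC(0-inf) ratio is the reciprocal of the CL/F ratio, which gives a programming check.
3. Report Tmax as median and range plus counts of early and late peaks, with cut-points fixed in advance to match the sampling windows. Use no t-test and no Hodges-Lehmann difference.
4. Remove the log-rank p-value from 6.9.2.1, or list it and any other retained comparison in 6.11 as exploratory and outside the protocol.
5. Correct the figure axis notes from mg/mL to ng/mL.

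The cost is SAP text, shells and a little programming. No data collection changes. Two cautions apply: the as-observed AUC and Cmax ratios must be labelled as reflecting dose as well as formulation, and intervals from 15 per arm may be wide.
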